5.0 Subject Disposition

For ITT_A, ITT_B, ITT_C, ITT_D and ITT_E populations, a summary of subject accountability will be provided where the number of subjects in each of the following categories will be summarized for each treatment group:

- Subjects randomized/enrolled;
- Subjects who took at least one dose of study drug;
- Subjects who completed protocol-specified treatment;
- Subjects who prematurely discontinued study drug;
- Subjects who prematurely discontinued from study.

Number and percentage of subjects who discontinued study drug and who withdrew from the study will be summarized by reason (primary reason and all reasons) for each

treatment group as well as for all treatment groups combined. Subjects with multiple reasons for premature discontinuation will be counted once in the calculation of the number and percentage of total discontinuations.

In addition, the above subject disposition will be summarized for ITT population by each cohort, as well as for all subjects combined.

6.0 Study Drug Duration and Compliance

For the safety populations (SA_A, SA_B, SA_C and SA_D), duration of treatment will be summarized for each treatment group. Duration of treatment is defined for each subject as last dose date minus first dose date + 1. Duration of treatment will be summarized using the number of subjects treated, mean, standard deviation, median, minimum and maximum. In addition, the number and percentage of subjects in each treatment duration interval (≥ 4 weeks, ≥ 8 weeks, ≥ 12 weeks, ≥ 20 weeks, ≥ 28 weeks, ≥ 36 weeks, ≥ 44 weeks, ≥ 52 weeks) will be summarized.

Treatment compliance will be summarized for SA_A by treatment group. Treatment compliance is defined as the number of tablets actually taken divided by the number of tablets that should have been taken. Percent compliance will be summarized.

7.0 Demographics, Baseline Characteristics, Medical History, and Prior/Concomitant Medications

Demographics and Baseline characteristics will be summarized for the ITT_A, ITT_B, ITT_C and ITT_E populations overall and by treatment group. Medical history, prior and concomitant medications will be summarized for the ITT_A population overall and by treatment group. Categorical variables will be summarized with the number and percentage of subjects; percentages will be calculated based on the number of non-missing observations. Continuous variables will be summarized with descriptive statistics (number of non-missing observations, mean and standard deviation, median, minimum and maximum).

7.1 Demographics and Baseline Characteristics

Continuous demographic variables include age, weight, height, and body mass index (BMI). Categorical demographic variables include:

- Sex (Male, Female)
- Age Group 1 (< 18 year, ≥ 18 years - < 40 years, ≥ 40 years - < 65 years, ≥ 65 years)
- Age Group 2 (≤ median, > median)
- Weight Group (≤ median, > median)
- BMI Group (normal: < 25 kg/m², overweight: ≥ 25 - 30 kg/m², obese: ≥ 30 kg/m²)
- Ethnicity (Hispanic or Latino, not Hispanic or Latino)
- Race (White, Black/African American, American Indian/Alaska Native, Native Hawaiian or Other Pacific Islander, Asian, Other)
- Region (US, ex-US)
- Tobacco user (current, former, never, unknown)
- Alcohol user (current, former, never, unknown)

Continuous baseline or disease characteristics variables include:

- Disease duration (years)
- Full Mayo score and its components (stool frequency subscore, rectal bleeding subscore, Physician Global Assessment, and endoscopy subscores)
- Partial Mayo score
- Adapted Mayo score
- hs-CRP (mg/L)
- Fecal Calprotectin (µg/g)
- IBDQ total and domain score
- Short Form 36 Health Survey (SF-36) and its components
- European Quality of Life 5 Dimensions 5 Levels (EQ-5D-5L)
- Functional Assessment of Chronic Illness Therapy-Fatigue (FACIT-F)

- WPAI and its components
- Ulcerative Colitis Symptoms Questionnaire (UC-SQ)

Categorical baseline or disease characteristics variables include:

- Bio-IR status (Bio-IR, non-Bio-IR),
- Prior exposure to biologic therapy (yes, no) for non-Bio-IR
- Number of prior biologic treatments (≤ 1 or > 1) for Bio-IR
- Prior exposure to anti-TNF (yes, no)
- Baseline corticosteroid use (yes, no)
- Baseline immunosuppressant use (yes, no)
- Baseline aminosalicylates use (yes, no)
- Baseline Adapted Mayo score (≤ 7 , > 7)
- Baseline Full Mayo score (≤ 9 , > 9)
- Baseline hs-CRP (≤ 5 mg/L and > 5 mg/L)
- Disease duration Group 1 (≤ 3 years, > 3 years)
- Disease duration Group 2 (\leq median, $>$ median)
- Disease extent (rectosigmoid, left-sided, extensive/pancolitis)

7.2 Medical History

Medical history data will be coded using the Medical Dictionary for Regulatory Activities (MedDRA). The actual version of the MedDRA coding dictionary will be noted in the statistical tables and clinical study report. The number and percentage of subjects in each medical history category (by MedDRA system organ class and preferred term) will be summarized overall and by treatment group for the ITT_A population. The system organ class (SOC) will be presented in alphabetical order, and the preferred terms will be presented in alphabetical order within each SOC. Subjects reporting more than one condition/diagnosis will be counted only once in each row (SOC or preferred term).

7.3 Prior and Concomitant Medications

Prior and concomitant medications will be summarized by generic name for the ITT_A population. A prior medication is defined as any medication taken prior to the date of the first dose of study drug in the Induction Studies. A concomitant medication is defined as any medication that started prior to the date of the first dose of study drug in the Maintenance Study and continued to be taken after the first dose of study drug or any medication that started on or after the date of the first dose of study drug, but not after the date of the last dose of study drug + 1 day. The number and percentage of subjects taking medications will be summarized by generic drug name based on the World Health Organization (WHO) Drug Dictionary for both prior and concomitant medications.

8.0 Efficacy Analyses

8.1 General Considerations

The primary and secondary efficacy endpoints will be analyzed based on ITT_A population as defined in Section 4.0. The primary and ranked secondary efficacy endpoints as specified in Section 3.1 and Section 3.2 will be tested with graphical multiplicity adjustment to ensure a strong control of family-wise type I error rate at significance level $\alpha=0.05$ (2-sided).

For analyses based on ITT_A population, unless otherwise specified, categorical variables will be analyzed using Cochran-Mantel-Haenszel (CMH) test, stratified by Bio-IR status (Bio-IR or Non-Bio-IR) at the Baseline of Induction Study, clinical remission status at Week 0 (yes or no), and corticosteroid use at Week 0 (yes or no). Any subject who was randomized under the wrong stratum will be analyzed according to the actual stratum the subject belongs to. Continuous variables collected longitudinally will be analyzed using Mixed-Effect Model Repeat Measurement (MMRM) model. Continuous variables collected at only one post-baseline visit will be analyzed using an Analysis of Covariance (ANCOVA) model. MMRM model includes the categorical fixed effects of treatment, visit and treatment-by-visit interaction, randomization stratification factors (Bio-IR status (Bio-IR or Non-Bio-IR) at the Baseline of the Induction Study, clinical remission status at

Week 0 (yes or no), and corticosteroid use at Week 0 (yes or no)), and the continuous fixed covariates of Baseline measurements. An unstructured variance covariance matrix (UN) will be used. If the model cannot converge, autoregressive (1) covariance structure matrix will be used. The parameter estimations are based on the method of restrictive maximum likelihood (REML). The fixed effects will be used to report model-based means at corresponding visits. ANCOVA model includes the categorical fixed effects of treatment, randomization stratification factors (Bio-IR status: Bio-IR or Non-Bio-IR) at the Baseline of the Induction Study, clinical remission status at Week 0 (yes or no), and corticosteroid use at Week 0 (yes or no)), and the continuous fixed covariates of Baseline measurements.

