Appendix E. Study Activities (Substudy 3)

Activity	Baseline of Substudy 3 ^a	Week 4	Week 8	Week 12	Week 20	Week 28	Week 36	Week 44	Week 52/ Premature Discontinuation Visit	Unscheduled Visit ^b	30-Day Follow-Up ^c
Informed Consent	X ^d										
Prior and Concomitant Medications [#]	X	X	X	X	X	X	X	X	X	X	
Physical Exam ^{e,+}	X	X	X	X	X	X	X	X	X	X	
Vital Signs ^{f,#}	X ^f	X	X	X	X	X	X	X	X ^f	X	
Schedule Endoscopy [#]								X			
Endoscopy/Biopsy ^{g,+}	X								X		
12-Lead ECG ⁺	X								X		
Chest X-Ray ^{h,+}									X		
Chemistry and Hematology ^{i,+}	X	X	X	X	X	X	X	X	X	X	
Lipid Test ^{t,+}	X				X				X		
Urinalysis ^{l,+}	X	X	X	X	X	X	X	X	X	X	
Pregnancy Test ^{k,+}	X	X	X	X	X	X	X	X	X	X	X

Activity	Baseline of Substudy 3 ^a	Week 4	Week 8	Week 12	Week 20	Week 28	Week 36	Week 44	Week 52/ Premature Discontinuation Visit	Unscheduled Visit ^b	30-Day Follow-Up ^c
Review and document continued compliance with pregnancy avoidance recommendations in the source records with females of childbearing potential [#]	X	X	X	X	X	X	X	X	X	X	X
hs-CRP ⁼	X	X	X	X	X	X	X	X	X	X	
Latent TB Risk Assessment Form [#]				X					X		
PPD Skin Test or QuantiFERON-TB Gold Plus Test ⁺									X ⁿ		
Provide Stool Kit ^{n,#}	X	X		X				X			
Stool Sample (Fecal calprotectin) ^{n,=}	X	X	X		X				X		
Upadacitinib Concentration (PK assay) ^{o,=}	X						X		X		
HBV DNA PCR (For Japan subjects only) ^{p,+}		X		X	X	X	X	X	X		

Activity	Baseline of Substudy 3 ^a	Week 4	Week 8	Week 12	Week 20	Week 28	Week 36	Week 44	Week 52/ Premature Discontinuation Visit	Unscheduled Visit ^b	30-Day Follow-Up ^c
Reminder: Samples for exploratory research and validation studies (Optional – see Appendix F) [†]		X		X		X		X	X		
Mayo Score [#]	X								X		
Partial Mayo Score [#]	X	X	X	X	X	X	X	X	X	X	
Patient Questionnaires: IBDQ, SF-36, EQ-5D-5L, WPAI, PGIC, FACIT-F, UC-SQ, PGIS ^{q,†}	X								X		
Monitor Adverse Events ^{r,†}	X	X	X	X	X	X	X	X	X	X	X
Daily Diary Review ^{s,†}	X	X	X	X	X	X	X	X	X	X	
Study Drug Dispensing/Administration ^{t,u,†}	X	X	X	X	X	X	X	X			

EQ-5D-5L = European Quality of Life 5 Dimensions 5 Levels; FACIT F = Functional Assessment of Chronic Illness Therapy – Fatigue; IBDQ = Inflammatory Bowel Disease Questionnaire; PGIC = Patient Global Impression of Change; PGIS = Patient Global Impression of Severity; SF-36 = Short-Form 36; UC-SQ = Ulcerative Colitis Symptoms Questionnaire; WPAI = Work Productivity and Activity Impairment

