3.0 Endpoints

The induction baseline (thereafter referred to as Baseline) visit date is the date when the first dose of study drug is received during Induction Studies. The baseline value for a variable is defined as the last non-missing value on or before the date of the first dose of study drug during Induction Studies.

The maintenance baseline visit date is on the same day as the final visit in the Induction Studies (thereafter referred to as Maintenance Baseline). The maintenance baseline value for a variable is defined as the last non-missing value on or before the date of the first dose of study drug during Maintenance Study.

The terminologies and efficacy variables are defined as below:

- Mayo Score
 - **Full Mayo Score:** composite score of UC disease activity based on the stool frequency subscore [SFS] (0 – 3), rectal bleeding subscore [RBS] (0 – 3), physician's global assessment [PGA] subscore (0 – 3) and endoscopic subscore (0 – 3). This score ranges from 0 – 12 points with higher scores representing more severe disease.
 - **Partial Mayo Score:** Full Mayo score minus the endoscopic subscore.
 - **Adapted Mayo Score:** Full Mayo score minus the PGA subscore.
 - **Partial Adapted Mayo Score:** Adapted Mayo score minus the endoscopic subscore.
- Clinical Remission
 - **per Full Mayo Score:** Full Mayo score ≤ 2 with no subscore > 1 .
 - **per Adapted Mayo Score:** Adapted Mayo score ≤ 2 , with SFS ≤ 1 and not greater than baseline, RBS of 0, and endoscopic subscore ≤ 1 .
 - **per Partial Mayo Score:** Partial Mayo score ≤ 2 , with no subscore > 1 .
- Clinical Response
 - **per Full Mayo Score:** decrease in Full Mayo score of ≥ 3 points and $\geq 30\%$ from Baseline, PLUS a decrease in RBS ≥ 1 or an absolute RBS ≤ 1 .
 - **per Adapted Mayo Score:** decrease in Adapted Mayo score ≥ 2 points and $\geq 30\%$ from Baseline, PLUS a decrease in RBS ≥ 1 or an absolute RBS ≤ 1 .
 - **per Partial Mayo Score:** decrease in Partial Mayo score ≥ 2 points and $\geq 30\%$ from Baseline, PLUS a decrease in RBS ≥ 1 or an absolute RBS ≤ 1 .

- **per Partial Adapted Mayo Score:** decrease in Partial Adapted Mayo score ≥ 1 point and $\geq 30\%$ from Baseline, PLUS a decrease in RBS ≥ 1 or an absolute RBS ≤ 1 .
- **Endoscopic Improvement:** Endoscopic subscore of 0 or 1.
- **Endoscopic Remission:** Endoscopic subscore of 0.
- **Histologic Improvement:** decrease from Baseline in Geboes score.
- **Histologic Remission:** Geboes score < 2 .

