8.3.2 Continuous Endpoints

For continuous endpoints, missing data will be handled using the following approaches:

- The primary approach is Multiple Imputation Incorporating Return-to-Baseline to Handle Visits After UC-related Rescue Medication Use (RTB-MI). To assess the potential departures from the missing-at-random (MAR) assumption for visits after the intercurrent event of UC-related rescue medication use (see section 8.2.2), the Return-to-Baseline (RTB)^{4,5} approach which assumes subjects received UC-related rescue medication will have a washout "return to baseline" of any potential treatment effect, will be performed as following:
 - Step 1: after setting data after the intercurrent event of UC-related rescue medication use as missing, missing values due to all causes will first be imputed via MI under the MAR assumption.
 - Step 2: subject's efficacy assessments after the intercurrent event of UC-related rescue medication will be assumed to have returned to baseline. For each imputed dataset, missing change from baseline data due to the intercurrent event of UC-related rescue medication will be replaced by a value from a normal distribution $N(0, V_c)$, where V_c is the variance of change from baseline estimated from all observed values regardless of treatment groups, excluding those after UC-related rescue medication use.
 - Step 3: For each imputed dataset, the MMRM/ANCOVA model described in Section 8.1 will be applied to each completed set and the inference will be drawn using Rubin's combination rules (SAS proc MIANALYZE).
- MMRM/ANCOVA: Assuming any unobserved data (including the missing due to the intercurrent event of UC-related rescue medication use) can be considered as MAR, an MMRM/ANCOVA model excluding data after the

intercurrent event of UC-related rescue medication use will be performed as a sensitivity analysis.

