8.5 Secondary Efficacy Analyses

8.5.1 Key Secondary Efficacy Analyses

The key secondary endpoints are defined in Section 3.2. The estimands corresponding to the secondary efficacy endpoints are defined in Section 2.1. Details of the estimand definitions are outlined in Appendix E. For ITT_A population, the key secondary efficacy endpoints will be analyzed by comparing each upadacitinib treatment group and placebo group. The binary secondary endpoints will be analyzed by CMH and the corresponding analyses are defined in Section 8.3.1. The NRI-C will be the primary approach for missing data handling in the analyses of binary secondary efficacy endpoints. The NRI-NC approach will be used as sensitivity analyses.

Continuous secondary endpoints will be analyzed by ANCOVA model with RTB-MI approach to handle the missing data due to UC-related rescue medication use as described in Section 8.3.2.

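### Substudy 3 ANCOVA and MMRM models omit the continuous Week 0 score, a modest and avoidable loss of precision for ranked IBDQ and FACIT-F

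*SAP*

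**What the plan says.** The Substudy 3 SAP uses two baselines. Section 3.0 states: "The induction baseline (thereafter referred to as Baseline) visit date is the date when the first dose of study drug is received during Induction Studies". By contrast, Week 0 has its own name, Maintenance Baseline, and its own rule: "The maintenance baseline value for a variable is defined as the last non-missing value on or before the date of the first dose" (here, the first maintenance dose).

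Section 8.1 builds both models from treatment, Bio-IR status at induction, remission and steroid use at Week 0 as yes/no factors, "and the continuous fixed covariates of Baseline measurements". MMRM adds visit and treatment-by-visit. No continuous Week 0 score is listed.

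Ranked endpoints 8 and 12 (section 3.2) are changes from induction Baseline to Week 52 in IBDQ total score and FACIT-F. Section 8.5.1 sends them to this model: "Continuous secondary endpoints will be analyzed by ANCOVA model with RTB-MI approach". In 8.3.2, Step 1 says that "missing values due to all causes will first be imputed via MI under the MAR assumption", without naming the variables of that model. In Step 2, "missing change from baseline data due to the intercurrent event of UC-related rescue medication will be replaced by a value from a normal distribution", with mean zero and variance Vc.

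Protocol Appendix E marks the row "Patient Questionnaires: IBDQ, SF-36, EQ-5D-5L, WPAI, PGIC, FACIT-F, UC-SQ, PGIS" at Baseline of Substudy 3 and at Week 52/PD. The SAP uses the Week 0 score only in non-ranked change-from-Maintenance-Baseline analyses (sections 3.3 and 8.6).

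**The concern.** Change from induction Baseline to Week 52 is the sum of two parts: Baseline to Week 0, and Week 0 to Week 52. The first part is complete before re-randomised treatment begins, so for the maintenance comparison it is noise that a pre-randomisation covariate can partly remove. The induction score does this only indirectly. Week 0 remission is a dichotomy of stool frequency, bleeding and endoscopy, and so a coarse stand-in for a quality-of-life or fatigue score. The ranked analysis is a single-visit ANCOVA, so no repeated-measures structure brings the Week 0 score in by another route.

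At stake is the precision of two ranked comparisons, and adjustment for chance imbalance in Week 0 status beyond the two yes/no factors. Section 12.0 tests the ranked endpoints in order, starting from 0.025 per dose, so a miss at endpoint 8 could affect those below it. The weights are in a figure that is not available in the text, so this cannot be traced further.

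**Working it through.** **Plan's own figure.** Section 2.4 states power above 95% for the primary endpoint with 150 per arm, 12% versus 40%, at two-sided 0.025. Exact enumeration of Fisher's test gives 99.97%, so the figure reproduces. It concerns the CMH-analysed primary endpoint. The documents give no SD, effect size, correlation, rescue rate or power for IBDQ or FACIT-F, so every input below other than the 150 per arm and the 0.025 level is an assumption.

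**Closed form, no rescue, before the Week 0 factors.** Take correlations of 0.4 (Baseline–Week 0), 0.3 (Baseline–Week 52) and 0.5 (Week 0–Week 52). The partial correlation of Week 0 with Week 52 given Baseline is (0.5 − 0.4×0.3)/√[(1 − 0.16)(1 − 0.09)] = 0.38/√(0.84×0.91) = 0.435. Adding the score multiplies residual variance by 1 − 0.435² = 0.811, a reduction of 18.9%.

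**Simulation of the planned analysis.** The settings were:

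- 150 per arm, one dose versus placebo, 800 trials per setting, 30 imputations.
- ANCOVA on change with treatment, Baseline score, Bio-IR, Week 0 remission (40% of subjects, latent correlation 0.5 with the Week 0 score) and Week 0 corticosteroid use (35%, latent correlation −0.2), fitted with and without the Week 0 score.
- Rescued subjects' change redrawn from N(0, Vc), results combined by Rubin's rules, no other missing data.

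Effective n is 150/(1 − reduction). Power is for a hypothetical comparison that has 80% without the covariate: Φ[(2.241 + 0.842)/√(1 − reduction) − 2.241].

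| Rescued | Reduction, Week 0–52 r = 0.3 | r = 0.5 | r = 0.7 | Effective n per arm (r = 0.5) | 80% power becomes (r = 0.5) |
|---|---|---|---|---|---|
| 0% | 3.3% | 16.2% | 39.8% | 179 | 87.0% |
| 10% | 1.6% | 8.7% | 20.9% | 164 | 83.8% |
| 20% | 0.8% | 5.1% | 12.6% | 158 | 82.2% |
| 30% | 0.5% | 3.1% | 7.7% | 155 | 81.3% |
| 50% | 0.0% | 1.2% | 3.0% | 152 | 80.5% |
| 40% placebo, 15% active, outcome-related | 1.1% | 5.8% | 14.3% | 159 | 82.5% |

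For the first row: 150/0.838 = 179, and 3.083/√0.838 − 2.241 = 1.127, so power is 87.0%. The 16.2% sits just below the closed-form 18.9%, as expected once the Week 0 factors take up part of the information. The estimated treatment difference was the same with and without the covariate to within 0.01 SD.

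**Why the gain shrinks.** The redrawn values carry no Week 0 information. If a share π is replaced at random, the slope on the Week 0 score falls by (1 − π) and the variance it explains by (1 − π)². At 20% that is 0.64, so 16.2% would become 10.4% even with residual variance unchanged. Mixing in draws centred on zero also raises residual variance, which takes the gain down to about 5%.

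**Sensitivity to the set-up.** A simpler calculation (400,000 subjects per cell; Baseline score and Week 0 remission as the other covariates; mean change 1.5 SD) gave, for Week 0–52 correlations of 0.3 to 0.5, reductions of 2.8–17% with no replacement, 1.2–6.6% with 20% replaced and 0.5–3.0% with 40% replaced. The mean change in non-rescued subjects also matters. At correlations 0.4/0.3/0.5, moving it from 0 to 2.5 SD moved the gain from 10.0 to 6.7% at 10% rescue, from 4.8 to 2.2% at 30%, and from 4.6 to 2.7% at 40%/15% with rescue unrelated to outcome.

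**The case against.** The case against is that this is a preference. The planned ANCOVA is valid, is protected by re-randomisation, and already holds the baseline of the change score and two Week 0 factors. The two endpoints rank 8 and 12 of 12, and nothing in the documents shows that they lack power. The largest figures need zero rescue, the least credible setting in a placebo-controlled maintenance trial of responders where rescue is allowed. The rescue figures depend on the mean change and on how strongly rescue follows outcome, neither of which the documents supply. The simulation also leaves out other missing data, although subjects with confirmed loss of response may move to Study M14-533.

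Much of this stands as a limit on size. The no-rescue figure should not be read as the expected gain in the ranked RTB-MI analysis; it is the closest guide only for the ANCOVA sensitivity analysis that drops post-rescue data. The power column illustrates scale and is not a forecast for this trial. No gain was computed for any MMRM endpoint. The missing variable list in 8.3.2 is a separate gap in specification and does not itself show lost efficiency. None of it answers the central point: a relevant pre-randomisation score is scheduled and defined, yet unused in the ranked analyses. The mean-change dependence shifts the rescue figures by only a few points, and in no simulated setting did the covariate do harm.

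**Conclusion.** The concern holds as one of efficiency. The primary endpoint and the ten binary ranked secondaries use CMH and are untouched. At a Week 0–Week 52 correlation of 0.5, rescue in the range of 20 to 30% puts the loss for ranked IBDQ and FACIT-F at roughly 2 to 6% of variance once uncertainty in the mean change is allowed for. It is larger if rescue is rare or the score is strongly correlated over time, and close to nothing if half the subjects are rescued. The direction is firm; the size depends on correlations, rescue and mean change that the documents do not give. The change should be made because it costs almost nothing, not because the planned analysis is unsound.

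**What to change.** In section 8.1 of the Substudy 3 SAP, add the Maintenance Baseline value of the same variable as a second continuous covariate in the ITT_A ANCOVA and MMRM models. Keep the induction Baseline score, the existing factors and change from induction Baseline as the response. In 8.3.2, list the variables of the missing-at-random imputation step for RTB-MI and DBMI and include the same Week 0 value, so that imputation and analysis models agree.

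The cost is one degree of freedom, a line of text and a small change in code. No new data are needed, and the last-non-missing rule in 3.0 already says which value to use. The change should be fixed before unblinding, since a covariate added afterwards would carry little weight.
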